23 FEBRUARY 2017

[figure not shown]
Date

Principal Investigator

22 February 2017

Date

Core Laboratory Director

3/Mar/2017

Date

PROTOCOL VERSION AND AMENDMENT TRACKING

Version	Approval Date
1.0 Initial Release	16 Feb 2017

Protocol Summary

Study Design and Rationale

A prospective, open label, multi-center, single arm, observational study designed to evaluate the acute safety and device procedural success of the Sapphire II PRO Ø1.0 and 1.25 mm PTCA dilatation catheters in subjects with stenotic coronary arteries or bypass grafts during percutaneous coronary intervention.

Sixty (60) subjects will be treated at up to 5 U.S. sites with the Sapphire II PRO Ø1.0 and 1.25 mm PTCA dilatation catheters to pre-dilate coronary arteries or bypass grafts during their index procedure. All subjects will be screened according to the protocol inclusion and exclusion criteria and will be followed through hospital discharge.

Study Summary

Name of Company	OrbusNeich Medical, Inc.
Product	Sapphire II PRO Ø1.0, 1.25 mm PTCA dilatation catheters
Protocol Number	VP-0714
Protocol Title	Sapphire II- Pro A prospective, open label, multi-center, single arm, observational study designed to evaluate the acute safety and device procedural success of the Sapphire II PRO Ø1.0 and 1.25 mm PTCA dilatation catheters in subjects with stenotic coronary arteries or bypass grafts during percutaneous coronary intervention.
Planned Number of Subjects and Sites	Sixty (60) subjects will be enrolled at up to 5 U.S. sites.
Primary Endpoint	Device procedural success consisting of the following: 
 • Successful delivery, inflation, deflation and withdrawal of the study balloon • No evidence of vessel perforation, flow limiting dissection (grade C or higher) or reduction in TIMI flow from baseline related to the study balloon • Final TIMI flow grade of 3 at the conclusion of the PCI procedure
Secondary Endpoints	The following clinical endpoints will be measured through hospital discharge: 
 1. In-hospital Major Adverse Cardiac Events (MACE) 
 -- All death (cardiac and non-cardiac) -- Myocardial infarction (MI) -- Target Lesion Revascularization (TLR) 2. In-hospital stent thrombosis (ST) within the target vessel 3. Clinically significant arrhythmias (requiring intervention) Peri-procedural endpoints: 
 • Balloon rupture • Improvement in Minimum Lumen Diameter (MLD) following pre-dilatation with Sapphire II PRO 1.0 and 1.25 mm PTCA dilatation catheters (measured by QCA)
Randomization	Not Applicable

Follow-Up Schedule	Subjects will be followed through hospital discharge.
Required Medication Therapy	Anti-platelet medications should be prescribed according to the standard of care at each investigational site.
Clinical Inclusion Criteria	
 1. Subject is \geq 18 years of age. 2. Subject or a legally authorized representative must provide written informed consent prior to any study related procedures. 3. Subject must agree not to participate in any other clinical study during hospitalization for the index procedure that would interfere with the endpoints of this study. 4. Subjects must have a single or double vessel coronary artery disease and clinical evidence of ischemic heart disease, such as stable / unstable angina or silent ischemia.
Angiographic Inclusion Criteria	
 5. Subject must have de novo or restenotic lesion(s) in native coronary arteries or bypass grafts that are suitable for percutaneous coronary intervention. An embolic protection device must be used in all Saphenous venous grafts (SVG) interventions performed during the index procedure. 6. A maximum of two lesions, including at least one target lesion, in up to two coronary arteries. 7. Target and non-target lesions must be located in different coronary arteries or bypass grafts. 8. Target lesion(s) must have a diameter stenosis of $\geq 70\%$ by visual estimation and may include chronic total occlusions (CTO) 9. Treatment of non-target lesion, if any, must be completed prior to treatment of target lesion and must be deemed a clinical angiographic success by visual assessment.
Clinical Exclusion Criteria	
 1. Subject with a known hypersensitivity or contraindication to aspirin, heparin, bivalirudin, anti-platelet medications, or sensitivity to contrast media which cannot be adequately pre-medicated. 2. Subject with known diagnosis of an acute myocardial infarction (AMI) within 72 hours prior to index procedure. 3. Subject with known pregnancy or is nursing. Women of child- bearing potential should have a documented negative pregnancy test within 7 days before index procedure. 4. Planned or actual target lesion treatment with an unapproved device, atherectomy, laser, cutting balloon or thrombectomy during the index procedure. 5. A serum creatinine level > 2.0 mg/dl within seven days prior to index procedure. 6. Cerebrovascular accident (CVA) within the past 6 months. 7. Active peptic ulcer or active gastrointestinal (GI) bleeding within the past 6 months.

	8. Subject has a known left ventricular ejection fraction (LVEF) <30% (LVEF may be obtained at the time of the index procedure if the value is unknown, if necessary)
Angiographic Exclusion Criteria	
9. More than two lesions requiring treatment.
 
10. Unprotected left main coronary artery disease.(Greater than 50% diameter stenosis)
 
11. Coronary artery spasm of the target vessel in the absence of a significant stenosis.
 
12. Target lesion with angiographic presence of probable or definite thrombus.
 
13. Target lesion involves a bifurcation requiring treatment with more than one stent or pre-dilatation of a side branch >2.0 mm in diameter.
 
14. Non-target lesion to be treated during the index procedure meets any of the following criteria:
 
 • Located within a bypass graft (venous or arterial) • Left main location • Chronic total occlusion • Involves a bifurcation (e.g., bifurcations requiring treatment with more than 1 stent) • Treatment not deemed a clinical angiographic success
	
A maximum of two lesions, including at least one target lesion, may be treated during the index procedure.
 
Non-target lesion should be treated first and deemed a clinical angiographic success by visual assessment prior to treatment of the target lesion
 
The lesion identified as the Target lesion is intended to be dilated first during the index procedure with a Sapphire II PRO 1.0 or 1.25 coronary dilatation catheter

	
Non-Target Lesion
 
 • A maximum of one non-target lesion (in addition to one target lesion in a target vessel) may be treated in a non-target vessel with a commercial treatment during the index procedure and must occur prior to treatment of target lesion. • Treatment of non-target lesion must be deemed a clinical angiographic success for subjects to be eligible for enrollment into the study. • Target and non-target lesions must be located in different coronary arteries or bypass grafts. 
Target Lesion
 
 • Lesion that is to be treated with the study device during the index procedure. • Target lesions may be located in the same or different coronary arteries or bypass grafts. • Target lesion composed of multiple focal lesions that can be covered with one stent will be considered as a single lesion. • One Sapphire II PRO PTCA dilatation catheter may be used for treatment of two separate target lesions located in the same vessel. It is recommended that

treatment of the distal lesion occurs prior to treatment of a more proximal lesion.

Note: A separate Sapphire II PRO PTCA dilatation catheter must be used for treatment of each target lesion if located in separate target vessels.

Statistical Methods

Enrollment definition	A subject is considered enrolled in the study following provision of informed consent and upon insertion of the investigational device into a guide catheter.
Follow-up Schedule	Subjects will be followed through hospital discharge
Primary Statistical Hypothesis	Not applicable as the study is observational. Descriptive statistics only.
Sample Size	A sample size of sixty (60) subjects has been chosen in order to characterize the performance of the device. All enrolled subjects will be analyzed on an intent-to-treat (ITT) basis as well as per protocol criteria.

Investigator Statement

I have read the Protocol and Appendices and agree that it contains all necessary details for me and my staff to conduct this study as described. I will provide copies of this Protocol and all pertinent information to the study to the study personnel under my supervision. I will discuss this material with them and ensure they are fully informed regarding the study devices and the conduct of the study. I will make all reasonable efforts to adhere to the study Protocol.

2.1. Description of Investigational Device

The Sapphire® II PRO Coronary Dilatation Catheter is a percutaneous transluminal coronary angioplasty (PTCA) balloon catheter with a working length of 140cm. The proximal shaft is a PTFE coated stainless steel hypotube. Hydrophilic lubricious coatings are applied to the distal section. The semi-compliant balloons are made of Nylon 12, available in diameters from 1.0 and 1.25 mm and lengths from 5-15mm, and can be inflated by injecting dilute contrast media solution through the trailing hub of the catheter. The nominal inflation pressure is 6 ATM and the rated burst pressure is 14 ATM. One radiopaque platinum marker bands is centrally located within the balloon segment. The catheter is compatible with 5F or larger guiding catheters. The internal lumen of the catheter accepts a standard 0.014 inch PTCA guidewire. The proximal portion of the guidewire enters the catheter tip and advances coaxially out the catheter proximal port, thereby allowing both coaxial guidance and rapid exchange of catheters with a single standard length guidewire. Two marked sections are located on the hypotube shaft to indicate catheter position relative to the tip of either a brachial or femoral guiding catheter. The design of this dilatation catheter does not incorporate a lumen for distal dye injections or distal pressure measurements.

Sapphire II PRO Coronary Dilatation Catheter Size Matrix Ø1.0, 1.25mm:

Balloon Diameter (mm)	Balloon Length (mm)			
	5	8	10	15
1.00	X	X	X	X
1.25	X	X	X	X

2.2. Summary of Findings from Non-Clinical Studies

In Vitro bench testing and characterization of the Ø1.0,1.25mm Sapphire II PRO Coronary Dilatation Catheter has been undertaken according to the requirements of the *Guidance of Industry and FDA Staff – Class II Special Controls Guidance document for Certain Percutaneous Transluminal Coronary Angioplasty (PTCA) Catheters, September 8, 2010*. Likewise, biocompatibility testing was undertaken according to the recommendations found in the aforementioned PTCA guidance and *ISO 10993-1:2009, Biological evaluation of medical devices – Part 1: evaluation and testing*.

2.3. Summary of Known and Potential Risks and Benefits

2.3.1. Potential Risks

There is extensive clinical and commercial experience worldwide with cardiac catheterization and interventional procedures and it is expected that the surgical and procedural risks will not be significantly different in this clinical trial. The Food and Drug Administration has recently downgraded balloon angioplasty catheters from class III (high risk) to class II (special controls) medical devices.¹ However, since there were not predicate devices for low-profile, small diameter balloon angioplasty catheters, then it was specified that a clinical evaluation for these small diameter devices be conducted under an Investigational Device Exemption is appropriate.²

The Sapphire II PRO Ø 1.0 and 1.25 mm Coronary Dilatation Catheters received CE mark approval in the European Union on 03 FEB 2015 and market approval in Japan on 09 SEP 2014. These catheters have been commercially available outside the US since FEB 2015. An on-going, prospective post-market surveillance program continues to show these devices to be safe and effective.

2.3.2. Risk Management

The investigational plan is specifically designed to manage and minimize risks through careful subject selection, thorough training of investigators and adherence to the pre-determined time points to assess subject clinical status and regular clinical monitoring visits by Sponsor appointed monitoring personnel.

2.3.3. Potential Benefit

Predilatation of complex, highly stenosed lesions with low profile small diameter balloons to optimize lesion preparation prior to stent placement may facilitate procedural success. The Sapphire II PRO Ø 1.0 and 1.25 mm Coronary Dilatation Catheters have been designed for this purpose with a hydrophilically-coated tapered distal tip, optimal balloon folding for a low crossing profile, and a low-friction inner body to reduce guidewire resistance.

2.4. Statement of Trial Conduct

This study is intended to be conducted according to Good Clinical Practice (GCP) guidelines³, local regulatory requirements, and subject ethical treatment must be in accordance with the World Medical Association Declaration of Helsinki: Ethical Considerations for Medical Research Involving Human Subjects.⁴

2.5. Study Population

The target study population is subjects with evidence of ischemia and clinically indicated for one- or two-vessel revascularization procedures by percutaneous coronary intervention.

2.6. Summary of Relevant Literature

Three previous trials of small diameter PTCA catheters have been reported in the literature and on ClinicalTrials.gov using a similar assessment method as proposed in this study. These studies are summarized in the following table:

Study Device	Primary endpoint	Subjects	Reference
Emerge™ 1.20mm PTCA Dilatation Catheter; Boston Scientific	Device Procedural Success: (1) Successful delivery, inflation, and withdrawal of study balloon (2) No evidence of vessel perforation, flow limiting dissection, or reduction in flow from baseline from study balloon (3) Final TIMI flow grade of 3 at conclusion of PCI	60	NCT01635881 ⁵ K130391
Mini Trek Rx 1.20mm Dilatation Catheter; Abbott Vascular	Procedural Success (1) Successful balloon delivery and cross lesion (2) Successful balloon inflation and withdrawal (3) No vessel perforation, flow-limiting dissection, reduction in TIMI flow from baseline, and no significant arrhythmias after study balloon (4) Achieve final TIMI 3 flow after PCI	71	CROSS ⁶ NCT 01186198 K110617
Sprinter Legend Balloon Catheter; Medtronic Vascular	Procedural Success: (1) Delivery of the balloon to the target lesion (2) No evidence of perforation or dissection (3) Restoration of normal blood flow at the end of the procedure	51	NCT00961311 ⁷ K103095

All three small diameter angioplasty catheters were found to be associated with favorable acute safety and efficacy as Predilatation devices in balloon angioplasty procedures.

3. Trial Objectives and Purpose

To assess the acute safety and device procedural success of the 1.0 and 1.25mm diameter Sapphire II PRO dilatation catheter in its intended use for the initial dilatation of coronary artery or by-pass graft stenosis (>70% diameter stenosis).

4. Trial Design

A prospective, open label, multi-center, single arm, observational study designed to evaluate the acute safety and device procedural success of the Sapphire II PRO Ø1.0 and 1.25 mm PTCA dilatation catheters in subjects with stenotic coronary arteries or bypass grafts during percutaneous coronary intervention.

Sixty (60) subjects will be treated at up to 5 U.S. sites with the Sapphire II PRO Ø1.0 and 1.25 mm PTCA dilatation catheters to pre-dilate coronary arteries or bypass grafts during their index procedure. All subjects will be screened according to the protocol inclusion and exclusion criteria and will be followed through hospital discharge.

4.1 Selection and Withdrawal of Subjects

Once the subjects have signed the Institutional Review Board (IRB) approved study informed consent form (ICF) and research authorization forms (RA/HIPAA) and have met all general inclusion and exclusion criteria, the subjects will be considered eligible to be enrolled in the study to receive treatment with the either the 1.0 or 1.25 mm diameter Sapphire II PRO dilatation catheter. A subject is considered enrolled in the study upon insertion of the investigational device into a guide catheter. Upon enrollment, a subject identification number will be assigned to each subject in a consecutive manner within each clinical site.

4.2 Inclusion Criteria

4.2.1 Clinical Inclusion Criteria

- Subject is \geq 18 years of age.
- Subject or a legally authorized representative must provide written informed consent prior to any study related procedures.
- Subject must agree not to participate in any other clinical study during hospitalization for the index procedure that would interfere with the endpoints of this study.
- Subjects must have a single or double vessel coronary artery disease and clinical evidence of ischemic heart disease, such as symptomatic CAD, stable / unstable angina or silent ischemia.

4.2.2 Angiographic Inclusion Criteria

- Subject must have *de novo* or restenotic lesion(s) in native coronary arteries or bypass grafts that are suitable for percutaneous coronary intervention. An embolic protection device must be used in all Saphenous venous grafts (SVG) interventions performed during the index procedure.
- A maximum of two lesions, including at least one target lesion, in up to two coronary arteries.
- Target and non-target lesions must be located in different coronary arteries or bypass grafts.
- Target lesion(s) must have a diameter stenosis of $\geq 70\%$ by visual estimation and may include chronic total occlusions (CTO)
- Treatment of non-target lesion, if any, must be completed prior to treatment of target lesion and must be deemed a clinical angiographic success as visually assessed by the physician.

4.3 Exclusion Criteria

4.3.1 Clinical Exclusion Criteria

- Subject with a known hypersensitivity or contraindication to aspirin, heparin, bivalirudin, anti-platelet medications, or sensitivity to contrast media, which cannot be adequately pre-medicated.
- Subject with known diagnosis of an acute myocardial infarction (AMI) within 72 hours prior to index procedure.
- Subject with known pregnancy or is nursing. Women of child- bearing potential should have a documented negative pregnancy test within 7 days before index procedure.
- Planned or actual target lesion treatment with an unapproved device, atherectomy, laser, cutting balloon or thrombectomy during the index procedure.
- A serum creatinine level > 2.0 mg/dl within seven days prior to index procedure.
- Cerebrovascular accident (CVA) within the past 6 months.
- Active peptic ulcer or active gastrointestinal (GI) bleeding within the past 6 months.
- Subject has a known left ventricular ejection fraction (LVEF) $< 30\%$ (LVEF may be obtained at the time of the index procedure if the value is unknown, if necessary)

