4.4 Subject Withdrawal Criteria

Each enrolled subject shall remain in the study until completion of the required follow-up period, however, a subject's participation in any clinical study is voluntary and the patient has the right to withdraw at any time without penalty or loss of benefit. Conceivable reasons for discontinuation may include, but not be limited to, the following:

- Subject death
- Subject voluntary withdrawal
- Subject withdrawal by physician as clinically indicated
- Subject lost-to follow-up

The reason for subject discontinuation must be documented on the CRF and source documents. The Primary Investigators must also report all subject discontinuations to their IRB, MEC, or HREC as defined by their Institution's procedure.

5 Treatment of Subjects

A maximum of two lesions, including at least one target lesion, may be treated during the index procedure.

Non-target lesion should be treated first and deemed a clinical angiographic success by visual assessment prior to treatment of the target lesion.

The lesion identified as the Target lesion is intended to be dilated first during the index procedure with a Sapphire II PRO 1.0 or 1.25 coronary dilatation catheter.

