7.3 Unanticipated Adverse Device Effects

Per United States Code of Federal Regulations (CFR) Title 21, Part 812.3, an unanticipated ADE (UADE) is any serious adverse effect on health or safety or any life-threatening problem or death caused by or associated with a device, if that effect, problem, or death was not previously identified in nature, severity, or degree of incidence in the investigational plan or application (including a supplementary plan or application) or any other unanticipated serious problem associated with a device that relates to the rights, safety, or welfare of subjects.

8 Device Failure and Device Malfunction

A device has failed or malfunctioned if it is used in accordance with the IFU/IB but does not perform according to the IFU/IB and negatively impacts the treatment.

Device deficiencies and other device issues should not be reported as AEs. Instead, they should be reported on the appropriate CRF per the study CRF Completion Guidelines. If an AE results from a device deficiency or other device issue, the AE should be reported on the appropriate CRF.

9 Statistics

This study is designed as a single-arm observational trial. The study sample size is based upon treatment of a reasonable number of subjects with the study device to provide a reliable and meaningful assessment of device performance, rather than based upon any statistical hypothesis of an endpoint.

All statistical analyses will be performed on an intent-to-treat basis. The baseline demographic and lesion characteristics and angiographic and clinical outcomes will be evaluated by descriptive statistics. These calculations will be performed under the assumption that the data are in a normal distribution. All enrolled subjects will be analyzed on an intent-to-treat (ITT) basis as well as per protocol criteria.

10 Direct Access to Source Data/Documents

- 10.1 The Investigator and the associated institution will permit direct access to source data/documents for study-related monitoring, audits, IRB review and regulatory inspections.

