11.3 Protocol Deviations

It is the Investigator's responsibility to ensure that there are no deviations from the protocol in full compliance with all established procedures of the IRB/MEC/HREC. The Investigator will not deviate from the protocol for any reason except in cases of medical emergencies, when the deviation is necessary to protect the life or physical wellbeing of the subject. All deviations must be reported to the Sponsor. The occurrence of protocol deviations will be monitored by the Sponsor or designee. Investigators will inform their IRB/MEC/HREC of all protocol deviations in accordance with their specific IRB/MEC/HREC reporting policies and procedures.

In the event that an Investigator does not comply with the Investigator Agreement or protocol, the Sponsor will notify the Investigator of the site's non-compliance. Continued non-compliance may result in further escalation in accordance with the Sponsor's SOP.

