11.9 Executive Committee

The Executive Committee is comprised of the Principal Investigator, Core Laboratory Director, and the Sponsor Vice-President of Clinical and Regulatory Affairs, or their designees. This committee will oversee general aspects of the study. This oversight includes review of the final protocol, ongoing monitoring of the general data collection, and review and consideration of implementation or operational issues that may arise and warrant a protocol amendment or other corrective action. The Executive Committee will also approve policy regarding presentations and/or publications.

12 Ethics

All subjects must provide written informed consent in accordance with the Site's IRB, using an IRB-approved informed consent form. The final eligibility for the trial will be the final pre-intervention angiographic qualification.

Study-specific procedures must not be performed until a signed informed consent has been obtained. The Investigator/designee, who has been trained on the protocol, will explain the nature and scope of the study, potential risks and benefits of participation, and answer questions from the patient.

All subjects are to be fully informed and study conduct must be in accordance with the World Medical Association Declaration of Helsinki: Ethical Considerations for Medical Research Involving Human Subjects.²

13 Data Handling and Record Keeping

Qualified study staff at each site will perform primary data collection from source document reviews. The Sponsor or their delegate will perform clinical monitoring, including review of CRFs with verification to the source documentation.

This study will use a CRF to collect study specific data. Before initiation of the trial, the investigator's site staff members who will be entering data will receive training on the completion of the CRF.

During monitoring visits, the site will ensure that access is available to the patient EMR for the clinical research associate (CRA), so that the CRA may verify the data entries in the CRF against source documentation.

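### Does barring actual use of listed devices during the index procedure let a post-enrolment event decide who is in the analysis?

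*Protocol*

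**What the plan says.** Protocol Section 4.3.1 excludes subjects with "Planned or actual target lesion treatment with an unapproved device, atherectomy, laser, cutting balloon or thrombectomy during the index procedure". The Protocol Summary carries the same item.

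Three statements fix when eligibility and enrolment are settled:

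- Section 4.1, on eligibility: subjects who have consented and "have met all general inclusion and exclusion criteria, the subjects will be considered eligible to be enrolled in the study".
- Section 4.1, on enrolment: "A subject is considered enrolled in the study upon insertion of the investigational device into a guide catheter". Section 5.3.1 and SAP Section 4.1 agree.
- Section 12 (Ethics): "The final eligibility for the trial will be the final pre-intervention angiographic qualification".

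The index procedure begins at sheath insertion (Section 5.3.3) and ends when the guide catheter is removed after final angiography (Section 5.3.4). On the order of treatment, Section 5 says: "The lesion identified as the Target lesion is intended to be dilated first during the index procedure", using the study balloon.

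On analysis sets, Protocol Section 9 and SAP Section 7.1 both state: "All enrolled subjects will be analyzed on an intent-to-treat (ITT) basis as well as per protocol criteria". Neither gives the per-protocol criteria. On departures from the protocol, Section 11.3 says: "All deviations must be reported to the Sponsor".

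**The concern.** An exclusion criterion should be answerable when the subject enters. Here, half of the criterion refers to what is actually done to the target lesion at any time up to guide catheter removal. Since the study balloon is meant to go first, another device on that lesion would usually come later, after enrolment. A correctly enrolled subject could then meet an exclusion criterion in retrospect.

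That would matter if the per-protocol set were built from the eligibility criteria, which is a common approach and is not ruled out. Suppose the study balloon cannot be delivered or inflated, which is a primary endpoint failure under Section 6.1, and the operator turns to a listed device. Removing that subject means selecting on a consequence of the outcome, and the per-protocol success rate would rise for reasons unrelated to eligibility at entry. With membership undefined, the rule could also be settled after outcomes are known.

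**Working it through.** **Timing.** Put in order, the defined points are:

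1. Sheath insertion: index procedure starts (5.3.3).
2. Angiographic eligibility confirmed (5.3.3).
3. Study balloon enters guide catheter: enrolment (4.1).
4. Study balloon used on the target lesion (5, 5.3.3).
5. Any further target lesion treatment.
6. Guide catheter removed: index procedure ends (5.3.4).

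Actual use between points 1 and 3 precedes enrolment and can be assessed at entry. Actual use at point 5 cannot. So the criterion agrees with Section 4.1 for the first interval and overreaches only for the second. The Section 12 sentence concerns the angiographic qualification, while this item is listed as a clinical criterion, so that conflict is weaker still. The eligibility lists mix entry and conduct rules elsewhere too: the inclusion list in 4.2.2 requires embolic protection in vein graft interventions performed during the index procedure.

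**Who is analysed.** Intent-to-treat is all enrolled subjects (Protocol 9, SAP 7.1), and enrolled subjects stay in the study through follow-up (Protocol 4.4). Meeting the criterion at point 5 does not remove anyone from that set.

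**Size of a per-protocol shift.** The plan has no figure to reproduce: 60 subjects is not derived from a hypothesis, and no failure rate or rate of listed-device use is given. The failure counts below are assumptions. With f failures in 60 and k of them dropped:

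- intent-to-treat rate = (60 − f)/60
- per-protocol rate = (60 − f)/(60 − k)

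For f = 6, intent-to-treat is 54/60 = 90.0% (exact 95% CI 79.5 to 96.2).

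| Failures dropped (k) | Per-protocol | Rate |
|---|---|---|
| 0 | 54/60 | 90.0% |
| 1 | 54/59 | 91.5% |
| 2 | 54/58 | 93.1% |
| 3 | 54/57 | 94.7% |
| 4 | 54/56 | 96.4% |
| 5 | 54/55 | 98.2% |
| 6 | 54/54 | 100% |

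Each dropped failure adds about 1.5 to 1.8 points. The interval around the intent-to-treat rate is 96.2 − 79.5 = 16.7 points wide.

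Other assumed cases:

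- f = 3: intent-to-treat 57/60 = 95.0%; dropping 1, 2 or 3 failures gives 96.6%, 98.3% or 100%.
- f = 9: intent-to-treat 51/60 = 85.0%; dropping 3 or 6 failures gives 51/57 = 89.5% or 51/54 = 94.4%.
- f = 6, three successes dropped instead: 51/57 = 89.5%, slightly below intent-to-treat.
- f = 6, two failures and two successes dropped: 52/56 = 92.9%.

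The shift can be nil, slightly downward, or upward. The 10-point maximum for f = 6 needs all six failures to be followed by a listed device and all six to be dropped.

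**The case for a change.** The best case for a change is that the per-protocol analysis is promised in the Protocol Summary, Protocol Section 9 and SAP Section 7.1, and its membership is nowhere fixed. The tables would not expose a problem: the SAP shells have no row for listed devices, and the deviation row in Table 4 is a bare yes or no. Part of SAP Section 7.2 is written in the past tense, which gives no assurance that the rule was set before the data were seen. A remedy would cost a phrase in the protocol and a few sentences in the SAP.

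The textual points stand: the criterion cannot be fully certified at enrolment, and the per-protocol set is undefined. The step from there to a needed change is weaker, for three reasons.

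- The exposure comes from the missing per-protocol definition, not from the word *actual*. If later use were reclassified as a deviation, a per-protocol set could equally exclude deviations, so rewording the criterion would not remove it.
- A rule that no later use may ever remove a subject is not plainly better. The primary endpoint includes final TIMI 3 flow at the end of PCI. Where a listed device follows a successful study balloon, final flow reflects both devices, and leaving such a subject out of a per-protocol set is defensible while intent-to-treat retains them.
- Dropping a study-balloon failure solely because a listed device followed would be poor practice. It would also show: intent-to-treat is reported on all enrolled subjects, so the two denominators would differ.

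**Conclusion.** No change to the plan is needed. The criterion overreaches in time, but only in part, and following the plan as written still gives a sound primary result. The intent-to-treat set is unaffected, there is no hypothesis or threshold for a per-protocol figure to influence, and none of the nine table shells has a per-protocol column.

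Harm requires three things that the documents do not state: a per-protocol set built on this criterion, listed devices used after the study balloon, and that use concentrated among failures. If all three held and 6 of 60 subjects failed, the per-protocol rate would move by about 1.5 to 1.8 points per dropped failure; its true size cannot be known from the documents. The missing definition is a detail that an analyst would settle when the set is drawn up, with deviations already reportable under Section 11.3. How to treat successes followed by a listed device is a judgement on which reasonable statisticians differ. This conclusion rests on intent-to-treat remaining the main analysis, as both documents state. It takes no view on which devices may be used clinically.
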